Therefore, this study aimed to understand the level of OK lens spoilage by fitting OK lenses on study participants, who are willing to wear lenses for a duration of one year. The lenses used in the study will be Menicon Z Night lenses (material: Tisilfocon A), registered with the Therapeutic Goods Administration (TGA) under ARTG entry 226883, and approved for overnight wear for myopia correction. Lens spoilage, including surface scratches and deposition, will be assessed at three time points: at lens dispensing, after 6 months of wear, and after 1 year of lens wear using established methods. In this study, we determine to explore the association between OK lens replacement schedules and keratitis risk. By tracking lens spoilage, patient symptoms, and clinical indicators of infection over 12 months, we intend to gather preliminary data on infection

risk. Given the difficulty of detecting keratitis with a small sample, we will use lens spoilage indicators as proxies for risk. We will also track all eye-related adverse events. While we may not establish a definitive keratitis rate, our approach will generate valuable insights on factors affecting OK lens-related health and guide future research on optimal replacement schedules to reduce keratitis risk.

Possible Risks

In this research, lens prescribing and fitting procedures, clinical assessments and follow-up care will be conducted as per the guidelines provided by the lens manufacturer (Menicon Pty Ltd). Regarding the risks, studies have demonstrated OK lenses are safe to use when fitted correctly by an eye care professional following the manufacturer's instructions.⁹

During the study, lens wearers may experience possible temporary adherence of the contact lenses to the eye surface, mild irritation and discomfort due to lens edges rubbing against the eyelid margin or an allergic reaction to lens solution. The risk of these complications is minimal when the study is monitored by a registered optometrist. While there is an exceptionally rare but possible risk of developing corneal infection and this risk is significantly lower with rigid contact lenses than a soft contact lens.

Hypothesis

We hypothesize that the OK lens spoilage, including scratches and surface deposits, as well as eye discomfort levels, will progressively worsen across the visits at baseline visit, 6 months and 12 months visit.

II. STUDY OBJECTIVES

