Objective: This study aims to assess the levels of lens spoilage under standard wear and disinfection practices in order to determine the optimal lens replacement frequency of OK lenses. Further, this study will evaluate the health of anterior surface of the eye and lens comfort levels during one-year overnight use of OK lenses.

III. STUDY DESIGN

The proposed study uses a *prospective, observational quasi-experimental research design* where the contact lens spoilage from same participants will be observed over the time before and after contact lens wear. This design is well-suited for monitoring real-world lens wear and eye health outcomes. The term "quasi-experimental" suggests that the non-randomized, single group study, which is appropriate for this type of longitudinal observations studies.

Individuals (between 18 to 40 years of age) with a refractive error between -1.00 and -4.00D of sphere and astigmatism $\leq 2.50D$ will be recruited in the study. The eligible participants will receive study OK lenses during the dispensing visit, following the screening visit. Participants will attend total eight visits, including a follow up visit 2 weeks after the lens cessation which will

allow to assess the recovery or stabilization of eye surface measurements. At each visit, the anterior surface of the eye and comfort levels will be assessed using clinical microscope and by administering questionnaires. Further, lens fit assessment and care regimen compliance will be monitored closely. A photographic method will be used to qualitatively assess lens spoilage at each visit. Furthermore, during the lens dispensing visit, the 6-month visit, and the 1-year visit, lens deposition will be quantitatively evaluated using established standard laboratory procedures. This will allow us to investigate the long-term changes in the eye surface during the OK lens wear and to determine their association with eye discomfort. Additionally, the levels of lens spoilage at different time points and their association with eye discomfort will determine the optimal replacement schedule of OK lens.

Participants will be monitored for:

- Signs of eye surface changes (e.g., corneal staining, conjunctival health).
- Contact lens comfort measured using standardized surveys (e.g., OSDI, CLDEQ-8).
- Lens spoilage (e.g., surface scratches, protein deposition).

Outcomes:

- **Primary outcome:**
 - OK lens spoilage grading scores.
- **Secondary outcomes:**

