Potential participants will be provided with Participant Information Sheets and Consent form (PISCF) to read, outlining the potential risks and benefits. There will be an opportunity to clarify details regarding the research study before participating. Interested participants, who contacted the investigators will be provided with PISCF through emails. All participants will be above the age of 18 years and will have adequate English language to be able to sign their consent for the study. The informed consent information sheet is attached.

Participants will be given at least 24 hours to review the PISCF before the screening visit. If they have any questions, they can contact the researchers. Written consent will be obtained at the screening visit, where participants will return the signed PISCF to the investigators. Only after consent is provided will the screening visit proceed.

Enrolment Procedure

The participant will only be considered enrolled into the study after the informed consent process has been completed and the participant has met all inclusion criteria and none of the exclusion ones. The participant will receive a study enrolment number, and this will be documented on all study documents.

V. STUDY OUTLINE

Table 3. Study outline and visit details.

Procedures/ Data (Y/N)	Screening visit (60 min)	Baseline visit (45-60 min)	1-day visit (45-60 min)	7-days visit (45-60 min)	21-days visit (45-60 min)	6-months visit (45-60 min)	12-month visit (45-60 min)	2-wk lens cessation visit (45-60 min)
Visit Window	N/A	N/A	N/A	± 2 days	± 2 days	± 7 days	± 7 days	± 2 days
Informed Consent	Y	N	N	N	N	N	N	N
Meet Inclusion / Exclusion Criteria	Y	N	N	N	N	N	N	N
Questionnaires	N	Y	Y	Y	Y	Y	Y	Y
Visual Acuity	Y	Y	Y	Y	Y	Y	Y	Y
Refraction	Y	Y	Y	Y	Y	Y	Y	Y
Anterior Eye Health Check	Y	Y	Y	Y	Y	Y	Y	Y

Procedures/ Data (Y/N)	Screening visit (60 min)	Baseline visit (45-60 min)	1-day visit (45-60 min)	7-days visit (45-60 min)	21-days visit (45-60 min)	6-months visit (45-60 min)	12-month visit (45-60 min)	2-wk lens cessation visit (45-60 min)
Visit Window	N/A	N/A	N/A	± 2 days	± 2 days	± 7 days	± 7 days	± 2 days
Corneal Topography	Y	Y	Y	Y	Y	Y	Y	Y
OK Lens Parameter Selection	N	Y	N	N	N	N	N	N
Lens Fitting Assessment	N/A	Y	Y	Y	Y	Y	Y	N
Lens Spoilage Assessment (qualitative)	N/A	Y	Y	Y	Y	Y	Y	N
Lens Spoilage Assessment (quantitative – protein assay)	N/A	Y	N	N	N	Y	Y	N
Lens compliance using “O-K Wear Time Journal”	N/A	Y	Y	Y	Y	Y	Y	Y

VI. SAFETY

1. Study Procedure Risks:

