The investigators are mindful of the need to actively reflect upon the balance between benefits and risks of a project while it is being conducted and the degree to which continuation of the study is justified should an adverse event be reported. Thus, any adverse event will be reported and handled in accordance with HREC Adverse Event Reporting Guidelines.

5. Benefits of the research outweigh the risk of harm or discomfort:

Eye infections associated with orthokeratology (OK) lenses is generally considered a low-incidence risk, particularly with proper lens care and adherence to recommended replacement schedules. While investigators cannot guarantee the direct benefits from this research, the potential benefits may include clear vision without needing to wear glasses or contact lenses during the day. The benefit of participating in this research study will contribute to the development of strategies that are aimed to minimise severe form of eye disease associated with long-term use of spoiled OK lenses.

Early Termination

The techniques proposed have been applied by the same and different investigators previously in multiple clinical studies and have not ever resulted in termination of any of these studies due to adverse events, so this is very unlikely. However, consideration for early termination of the study would occur if a serious adverse event is reported or if all collected data were of insufficient quality for analysis after repeated attempts at improving recording techniques and methods.

VII. STATISTICAL CONSIDERATIONS.

Sample size calculations

We are planning a study with an ordinal data response variable from matched pairs of study participants. We estimate that the difference in the lens spoilage grading between matched pairs is normally distributed with a standard deviation 0.9. To detect a true mean difference of 1.90 between pairs, we will need 12 subjects to achieve 80% power, assuming a Type I error rate of 0.05. To account for a 20% dropout rate, a total of 16 participants will be recruited. We will keep screening until we have met that target. However, since this sample size was not determined using the exact methodology relevant to the current study, we will collect pilot data as part of the research. Based on the pilot data results, we will recalculate the final sample size to ensure the statistical power is appropriately adjusted for the use of orthokeratology (OK) lenses.

Statistical Analysis

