The study hypothesises that OK lens spoilage, including scratches and surface deposits, as well as eye discomfort levels, will progressively worsen across the visits at baseline visit, 6 months and 12 months visit. All the statistical methods will be aimed to address the given hypothesis.

Once all data are collected, different tests will be conducted to establish whether they follow normal distributions. This step will ensure us to choose the appropriate statistical test based on the data distribution. Continuous variables will be expressed as means \pm standard deviations, while categorical variable will be reported as medians and interquartile ranges (IQR). The time

effect (baseline, 6month and 12 month) and between-group differences in lens deposition levels, lens wettability scores, eye discomfort data from questionnaires, and eye surface changes will be tested with repeated measures ANOVAs (post-hoc tests) or Friedman test, with Bonferroni correction, where appropriate. This method will assess whether there are significant differences in spoilage across the three time points. If significant, post-hoc tests will help confirm if the worsening follows a progressive pattern from baseline visit to 12 months.

This study will use Spearman's correlation test to evaluate the correlations between the questionnaires scores (eye discomfort levels) and clinical test results (deposition and scratches). This correlation analysis will determine how these subjective and objective measures relate, further supporting the study hypothesis if a correlation is found. A value of $P < 0.05$ will be considered as significant. Furthermore, we determine to explore the association between OK lens replacement schedules and keratitis risk. By tracking lens spoilage, patient symptoms, and clinical indicators of infection over 12 months, we intend to gather preliminary data on infection risk. Given the difficulty of detecting keratitis with a small sample, we will use lens spoilage indicators as proxies for risk. We will also track all eye-related adverse events. While we may not establish a definitive keratitis rate, our approach will generate valuable insights on factors affecting OK lens-related health and guide future research on optimal replacement schedules to reduce keratitis risk.

VIII. STORAGE AND ARCHIVING OF STUDY DOCUMENTS.

Data format and storage location

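### The only stated time-effect test of lens spoilage uses baseline, 6 and 12 months; grades taken in the first weeks of wear, which could separate early coating from later build-up, get no formal test

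*Protocol*

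**What the plan says.** On when spoilage is graded, the protocol has two accounts.

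- **Every lens-wear visit.** The Summary and III. Study Design: "A photographic method will be used to qualitatively assess lens spoilage at each visit". The Follow-up visits item of the Detailed Study procedure repeats this for lens-wear visits. In Table 3 (V. Study Outline) the row that begins "Lens Spoilage Assessment (qualitative" is marked yes at baseline, 1, 7 and 21 days, 6 and 12 months.
- **Three visits.** I. Background, Rationale: spoilage, with scratches named explicitly, is "assessed at three time points: at lens dispensing, after 6 months of wear, and after 1 year of lens wear".

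On analysis, VII. Statistical Analysis tests the time "effect (baseline, 6month and 12 month) and between-group differences in lens deposition levels" and other outcomes by repeated measures ANOVA or Friedman test. It then describes this as a test of spoilage over three time points, with post-hoc tests to show whether worsening is progressive.

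Two further facts matter. The baseline lens is graded before and after in-clinic wear, and participants are trained in handling only afterwards, so it has had no overnight wear. The quantitative assessment item replaces the right lens at 6 months, because the original goes to the laboratory.

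**The concern.** The objective is to find the optimal replacement frequency. That depends on how spoilage changes with lens age. If a lens coats in its first nights and then stays level, age gives little reason to replace it; if spoilage builds steadily over months, age does. A level course is a realistic possibility, since participants receive a weekly protein remover (Table 2).

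The first interval in the stated test runs from a lens never worn overnight to one with six months of wear. A significant rise over that interval fits either course. The Rationale itself says that assessment at frequent intervals is needed, and the early grades are collected, but no formal test of them is stated.

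**Working it through.** **1. Which gradings fall outside the stated test.** The count depends on the visit list.

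- Table 3: graded after overnight wear at 1, 7 and 21 days, 6 and 12 months, so 5 visits. Outside the test: 3 of 5 (60%), all within the first 21/365 = 5.8% of the year.
- Follow-up visits item: 1, 7 and 14 days, 1, 6, 9 and 12 months, so 7 visits. Outside the test: 5 of 7 (71%), four in the first month plus the 9-month visit.

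The 1-day and 7-day visits are in both lists, so early worn-lens grades exist either way.

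**2. What each stated contrast contains.**

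- Baseline to 6 months: first-nights coating plus six months of build-up.
- 6 to 12 months: no first-nights coating for the left lens, whose age goes from 6 to 12 months. The right lens graded at 12 months is a replacement about 6 months old, so it says nothing about ageing beyond 6 months.
- Neither contrast shows when, within the first 6 months, a rise occurred.

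**3. Two courses that the three points cannot tell apart (assumed values, 0 to 4 scale, 6 months = 182 days).**

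- Early coating: 1.50 after one night, then 0.2 per 6 months. At 6 months 1.50 + 0.2 = 1.7; at 12 months 1.9; at day 21 about 1.50 + 0.2 × 20/182 = 1.52.
- Gradual: linear to 1.7 at 6 months, then slowing to 1.9. At day 21, 1.7 × 21/182 = 0.20.

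Both give 0, 1.7 and 1.9 at the analysed visits; at day 21 they differ by 1.32.

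**4. The plan's own figures.** There is none for the time course. The sample size section assumes that "the difference in the lens spoilage grading between matched pairs is normally distributed with a standard deviation 0.9" and states "To detect a true mean difference of 1.90 between pairs, we will need 12 subjects to achieve 80% power". That number does not reproduce: ((1.960 + 0.842) × 0.9/1.90)² = 1.76, and an exact two-sided paired t test has 79.4% power at n = 4 and 93.4% at n = 5. This is a separate matter. I borrow only n = 12 and SD 0.9 as a scale. At n = 12 the power for a 1.90 difference exceeds 99.9%, so a significant baseline-to-6-month result would be expected whatever the course of the rise.

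**5. Simulation.** One lens followed to 12 months, as for the left eye; n = 12; normal scores standing in for grades; participant SD 0.5; visit error SD 0.9/√2 = 0.64, so that a paired difference has SD 0.9; 5,000 runs. Friedman test at 0.05, paired t contrasts two-sided at 0.05/3. Assumed means at baseline, days 1, 7 and 21, and months 6 and 12:

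- A, first-night coating: 0, 1.9, 1.9, 1.9, 1.9, 1.9
- B, build-up by month 6, then level: 0, 0, 0, 0.2, 1.9, 1.9
- C, steady rise: 0, 0, 0.04, 0.11, 0.95, 1.9

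| Rejections (%) | A | B | C |
|---|---|---|---|
| Friedman, three points | 100 | 100 | >99.9 |
| Baseline to 6 months | 100 | 100 | 78.3 |
| 6 to 12 months | 1.6 | 1.5 | 78.4 |
| Day 1 to 6 months | 1.8 | 100 | 79.0 |
| Day 21 to 6 months | 1.6 | 99.9 | 65.4 |

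The first three rows are the stated analysis: A and B look the same, while C is told from A by the 6-to-12-month contrast. The last two rows use grades already collected, and they separate A from B.

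**The case against.** The three-point test matches the stated hypothesis, which is worsening at baseline, 6 and 12 months. Leaving the early aftercare visits out of a formal test is a defensible choice, and a secondary time-course analysis could sit in an unseen SAP. This stands as a reason to keep the test, not to rest replacement conclusions on it alone: the protocol itself fixes the time points for its primary outcome.

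Three stronger readings are tempting, and the document does not support them.

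- A reader might infer that the early grades are discarded. The text limits only the ANOVA or Friedman test to three visits. The descriptive summaries and the Spearman correlations are not so limited.
- A reader might infer that three points can never distinguish coating from build-up. The 6-to-12-month contrast contains no first-nights coating, and course C shows it detecting steady growth. The ambiguity remains when growth also nearly stops after 6 months, and for any question about intervals under 6 months.
- A reader might take the curves or rejection rates as estimates. No document figure gives a grade after one night or a deposit time course; the courses were chosen to show what can happen. The 60% likewise holds only under Table 3.

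It is also fair that early coating is an argument about deposits. Scratches need not follow it, so the two grades should be analysed separately.

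**Conclusion.** The concern holds in limited form. The Rationale conflicts with the sections that grade spoilage at each lens-wear visit. The stated test's first interval merges early coating with build-up over months. Its second interval avoids this, but informs on ageing beyond 6 months only through the left lens. No formal test of the early grades is stated, although they are collected and bear directly on the replacement objective.

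The size cannot be estimated from the document. It ranges from nothing, if spoilage rises steadily through 12 months, to a complete inability of the stated test to tell two opposite courses apart, if the rise is over by month 6. The conclusion assumes that the right lens graded at 6 months is the one dispensed at baseline, as the text implies. It concerns the graded outcome only: the laboratory assay is planned at just three visits, so early visits cannot be added there. The main test can still be run; this is an inexpensive improvement to what may be concluded about replacement.

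**What to change.** 1. In the Rationale, state that qualitative spoilage is graded at each lens-wear visit and that only the laboratory assay is confined to baseline, 6 and 12 months.
2. Reconcile the visit lists: the Summary, the opening of the Detailed Study procedure and Table 3 against the Follow-up visits item.
3. In Statistical Analysis, keep the three-point test of the stated hypothesis. Add a pre-set repeated-measures analysis (ordinal or linear mixed model) of deposit grades and, separately, scratch grades at all lens-wear visits, with time expressed as lens age per eye and eyes nested within participant.
4. Report two contrasts: (a) new lens to early wear; (b) a named early worn-lens visit to 6 months, using both original lenses, and to 12 months, using the left lens only. Base statements on build-up and replacement interval on (b).

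**Cost.** Wording and slightly more analysis; no new visits or measurements. The added contrasts need a multiplicity rule or a clear secondary label. With 12 to 16 participants, (a) may need a paired or descriptive summary if all new lenses grade 0, because an ordinal model could fail to fit. Precision is modest: with n = 12, SD 0.9 and two-sided alpha 0.05/3, a single paired contrast has 80% power for 0.97 grades, so a smaller change could be missed and a non-significant (b) should not be read as no build-up. The early reference visit should be named before the grades are seen; chosen later, the contrast would be exploratory.

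### The protocol does not say which comparisons establish progressive worsening; the claim needs both successive steps, each testable at 0.05, so correcting these tests for all visit pairs would only lose power

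*Protocol*

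**What the plan says.** Section VII of the protocol, Statistical Analysis, gives one hypothesis: spoilage and discomfort worsen progressively over the baseline, 6-month and 12-month visits. All methods are said to serve it. The time effect is tested by repeated measures ANOVA with post-hoc tests "or Friedman test, with Bonferroni correction, where appropriate". The next stage is that "If significant, post-hoc tests will help confirm if the worsening follows a progressive pattern from baseline visit to 12 months". The text gives no Bonferroni divisor, does not list the post-hoc comparisons and does not say which of them must be significant.

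The sample size paragraph appears in the Summary, in Section IV (Number of participants) and in Section VII. It assumes that the "difference in the lens spoilage grading between matched pairs is normally distributed with a standard deviation 0.9". The target is stated as "To detect a true mean difference of 1.90 between pairs", and the result is that "we will need 12 subjects to achieve 80% power, assuming a Type I error rate of 0.05". Then: "To account for a 20% dropout rate, a total of 16 participants will be recruited". The visits that the 1.90 compares are not named. Section VII adds that this size did not come from the methodology relevant to the study and will be recalculated from pilot data.

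**The concern.** Progression over three visits is a joint claim: worse at 6 months than at baseline, and worse again at 12 months than at 6. When every component test must succeed, the error rate of the joint claim cannot exceed the level of a single component test (the intersection-union principle). A Bonferroni correction protects against a claim made when any one of several tests succeeds, which is a different situation. Applied here, it makes a true progression harder to show and gives no error control that the claim needs.

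The missing rule also matters for interpretation. The study's objective is a replacement schedule, so spoilage that levels off after 6 months and spoilage that keeps growing lead to different conclusions. Only the 6-to-12-month comparison separates them, and nothing says it must be significant.

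**Working it through.** **1. The protocol's own figure.** Inputs: difference 1.90, SD 0.9, n = 12, alpha 0.05 (sidedness not stated; two-sided taken). The standardised difference is 1.90/0.9 = 2.11. For a paired t-test the non-centrality is 2.11 × √12 = 7.31, against a critical value t(11) = 2.20. Power is above 99.99%, not 80%; 5 subjects would give at least 80%. Twelve subjects give 80% at a standardised difference of about 0.89, that is 0.89 × 0.9 = 0.80 grade units. The stated 80% is therefore not reproduced. On dropout, 12/0.8 = 15 against the 16 stated, which is close.

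**2. False-positive rate of the both-steps rule.** The worst case is one large step and one truly null step. The joint claim is then false, and it is made only when the null step is significant in the worsening direction. By simulation with n = 12:
- each step at two-sided 0.05: about 2.5%
- each step at 0.05/3 = 0.0167: about 0.8%

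Both are below 5%, so the correction is not needed for this claim.

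**3. Power for both steps, with and without correction.** Assumptions that the protocol does not give: 1.90 is the whole-year change, it splits into 0.95 + 0.95, every paired change has SD 0.9, and the Bonferroni divisor is 3. Per step, the non-centrality is (0.95/0.9) × √12 = 3.66.
- At 0.05 (critical value 2.20): 91% per step.
- At 0.0167 (critical value 2.82): 78% per step.

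If all three paired changes (baseline–6, 6–12, baseline–12) have SD 0.9, the two steps must have correlation −0.5, because the year-change variance is 2 × 0.9² × (1 + r) and this equals 0.9² only at r = −0.5. Simulated power for both steps is then **83% uncorrected and 59% corrected**. An overall F test in front changes neither figure, as it is almost always significant here.

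**4. Sensitivity.** Hold the year-change SD at 0.9 and let the step SD follow as 0.9/√(2(1 + r)):

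| Correlation r | Step SD | Both steps, 0.05 each | Both steps, 0.05/3 each |
|---|---|---|---|
| −0.5 | 0.90 | 83% | 59% |
| −0.25 | 0.73 | 96% | 86% |
| 0 | 0.64 | 99% | 96% |

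An uneven split of 1.20 + 0.70 gives 68% against 44% at r = −0.5, and 93% against 82% at r = 0. With step SD 0.9, an even split, independent steps and 15 or 16 completers, corrected power is 80% or 85%. If 1.90 were the change in each half-year, corrected power would exceed 99.9%.

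**5. Plateau.** Put all 1.90 in the first six months and nothing after. The baseline–6 and baseline–12 comparisons are then both significant, even at 0.0167, in 98% to more than 99.9% of simulated trials (step SD 0.9, r from 0 to −0.5). These two results together therefore say nothing about continued worsening.

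**The case against.** The strongest reply is that the protocol contains no corrected both-steps rule. Bonferroni applies only where appropriate, in a sentence that also covers wettability, questionnaires and eye-surface changes, and the post-hoc tests merely help to confirm the pattern. Details could be left to an analysis plan. This stands in part: the correction is a likely reading, not a fixed one. But the protocol itself names the post-hoc tests as the means of confirming its only hypothesis, and as worded they cannot do so without a decision rule.

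A reader might infer that the plan's true power is about 60% instead of the stated 80%. The documents do not support that. The 80% is attached to one paired difference, and no power is stated for the three-visit pattern. The 59% needs a split, step SDs and a divisor that the protocol does not give, and step 4 shows how far it moves.

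A reader might also infer that the plan would report a plateau as progression. It might not: post-hoc tests on all visit pairs would include 6 to 12 months. The risk exists only because no rule requires that comparison.

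Three further replies stand. Bonferroni is conservative here, not invalid. Baseline to 12 months is a fair question in its own right for a replacement schedule, and correction is reasonable if each interval is interpreted separately. The sample size is also openly provisional; yet the planned recalculation names no target contrast, so it could repeat the mismatch.

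Finally, the right lens is replaced at 6 months (Section III, item 4), so for that eye the 6-to-12-month change is not within one lens. This does not affect the multiplicity argument, but a definition of the second step has to allow for it.

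**Conclusion.** The point holds as a missing and poorly matched decision rule, not as a demonstrated power shortfall. Two conclusions need no assumed effect size: progression requires both successive steps, and testing each at two-sided 0.05 keeps the false-claim rate at about 2.5%. If the three visit pairs are corrected, power is lost for no needed protection. The loss is 24 percentage points (83% to 59%) under an even split with SD 0.9 for every paired change and 12 completers, and about 3 points (99% to 96%) if the year-change SD is 0.9 and the steps are uncorrelated. Separately, the stated 80% is wrong on its own inputs and should not be kept as the power for a single paired change.

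**What to change.** In Section VII, Statistical Analysis:
- Define progressive worsening as both the baseline-to-6-month and the 6-to-12-month changes significant in the worsening direction, each at two-sided 0.05, uncorrected and without an overall test as a gate for this claim.
- Say that baseline to 12 months does not count towards the claim.
- Keep Bonferroni for any pairwise comparison interpreted on its own.

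In the Summary, Section IV and the Section VII sample size text:
- Correct the 80% figure, without restating it as the power for a single paired change.
- Say which visits the 1.90 compares.
- Base the planned pilot-data recalculation on the smaller of the two successive steps, with step sizes and SDs given as assumptions.

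The wording costs a few sentences and no extra data. The recalculated sample size may differ from 16 in either direction.
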